6.6 Expected Duration of Trial

The end of the trial is defined as database lock.

Each participant will remain in the study as long as their time to conception (up to maximum 12 months) and their full length of pregnancy until delivery (a total maximum of 21 months). In total a number of 328 pregnant patients will be included in the study. The total study duration is 108 months.

7 Trial Procedures

7.1 By Visit

The sequence of visits is outlined in the flowchart in section 4.3.

All patients participating in the HYPATIA trial will be seen pre-conception, then at least on a 3 monthly basis for medication refill until conception, and then once every trimester and post-partum according to a routine standard of care protocol (outlines in the assessment schedule outlined in section 4.3). This will enable face-to-face contact with patients to discuss any concerns. Patients will be advised to contact the research team to report any concerns about the treatment between trial visits.

SCREENING VISIT

- Not pregnant yet, but is actively planning pregnancy
- The patient will be screened for eligibility
- Presence of antiphospholipid antibodies will be confirmed

Pre-pregnancy	 Written informed consent Eligibility assessment Blood results can be obtained from routine blood results within 12 months arises to entroise the UVDATIA study. The following blood
	months prior to entering the HYPATIA study. The following blood results will be reviewed & have to be recorded in the patient notes and eCRF:
	 aPL antibodies including date of test, titers, units and reference range for 95th percentile used in local lab – repeat if necessary ENA antibodies
	 Baseline bloods (FBC, renal function and liver function) as standard of care bloods before IMP start – can be obtained from routine blood results within 3 months prior to entering the study
	 Demographic information (see options in 'Glossary of Terms") Height & weight Smoking status
	Physical exam (including lung and heart stethoscopy)Urine dip
	Blood pressure & PulseCurrent medication
	 Past medical and past pregnancy history eCRF information will be filled out

Women will not be pregnant at this stage but are actively trying to fall pregnant. In case a woman is pregnant but not known to be pregnant at recruitment but who subsequently is confirmed pregnant within next LMP, the patient will remain in the trial and these data will analyzed as 'intention to treat'.

Potential participants will be consented if they are happy to participate in the HYPATIA study and will be assessed for eligibility. Patient notes (either in paper or electronic form) are defined as the source data and all study relevant information will be captured in the patient notes and then transferred into the eCRF.

Blood results from blood tests taken prior to entering the study can be used within the timelines specified below. If a patient has had a positive test for antiphospholipid antibodies prior to study entry within 12 months of study entry, these results can be used and recorded into the eCRF (test date and normal range have to be provided). For the screening routine blood test (full blood count, kidney and liver profile) pre-trial results not older than 3 months can be used. On an individual basis these blood results can be updated, but this will be left for the discretion of the treating physician.

ONLY FOR WOMEN IN SELECTED CENTRES: Women in selected centres will be invited to donate blood samples at baseline, once pre-pregnancy, every trimester and post-partum for further studies funded by separately. This will be outlined in the Laboratory section.

BASELINE VISIT	
 Confirmation of eligibi Randomization IMP dispensation 	lity
	 Adverse events monitoring Current medication Eligibility confirmation Randomization & IMP dispensation – every 3 months From now the patient will be followed up on a three monthly basis not pregnant & will be advised to contact the study team onc pregnancy is confirmed. IMP will be dispensed on each of the 3 montly pre-pregnancy visits. Women will be instructed that they will be followed up on a 3 monthl basis from now. This is part of our standard of care protocol for women being treated at all centres and we expect our participatin centers to adapt this approach for the purpose of the HYPATIA tria Women will also be instructed to contact their local study team onc they fall pregnancy and will then be seen by the local study team for review. This is standard of care in these women, and will coincid with the HYPATIA study visits.
	Selected centres: bloods for additional research

 PRE-PREGNANCY VISITS (up to 4 visits) At this stage the patient is taking the IMP & is still actively planning to fall pregnant IMP re-dispensation Visits every 3 months until patient pregnant, max 4 times (a total of 12 months) 	

Once a patient becomes pregnant, the patient will be brought back to clinic. The 'pregnancy progress' will be recorded in the patient notes.

PREGNANCY follow up visit 1		
1 st Trimester visit (Gestational week 1 – 13+6)		
The patient has been allocated to either hydroxychloroquine or placebo and is pregnant. At this stage patients will require new trial medication, which should be handed out at this visit. The reason to supply the patient with new trial medication is to ensure sufficient trial medication for follow up visits.		
Pregnancy	 Information on pregnancy will be collected: IVF pregnancy Singleton, Twin or Triplet pregnancy How many weeks has patient taken trial medication Current gestation Estimated Date of Delivery Physical exam (including lung and heart stethoscopy) Blood test including full blood count, kidney and liver function to monitor for HCQ toxicity Selected centres: bloods for additional research 	
Medication	 All medications will be recorded. Compliance check (Kit number to be noted, date of current kit started & ended, number of tablets taken, number of tablets missed) IMP dispensation The patient will be asked to bring unused trial medication and empty packaging to each visit (number of tablets taken & number of tablets missed will be recorded), this will be collected, and a new supply will be given. 	
Adverse events & Adverse pregnancy events	Enquiry about adverse events including adverse pregnancy events. In case the patient has miscarried an 'adverse pregnancy events' form has to be filled out (not SAE).	

Participants who have fallen pregnant, will be seen on a regular basis in the pregnancy clinic. Information regarding the pregnancy will be documented in the patient notes and shall afterwards be transferred into the eCRF. In case a patient has had a miscarriage, information regarding the miscarriage will also be documented in the patient notes. The patient will be instructed to stop trial medication and to bring all spare trial medication to the next follow up visit. The remainder of the medication will then be counted and the results recorded in the CRF.

PREGNANCY follow up visit 2	
2 nd Trimester visit (Gestational week 14 – 26+6)	
Pregnancy	 Information on pregnancy will be collected: How many weeks has patient taken trial medication Current gestation Estimated Date of Delivery Physical exam (including lung and heart stethoscopy) Blood test including full blood count, kidney and liver function to monitor for HCQ toxicity

	Selected centres: bloods for additional research Record whether patient has had anomaly scan, record fetal growth and uterine artery Doppler results (results can be recorded at 2 nd or 3 rd trimester visit). Record FGR.
Smoking status	 Smoking status update
US growth scans	Depending on the individual patient one or more US scans have been performed during the second trimester. All available growth scan results will be recorded. Information will be obtained from maternity records.
Medication	 All medications will be recorded. Compliance check (Kit number to be noted, date of current kit started & ended, number of tablets taken, number of tablets missed) IMP dispensation The patient will be asked to bring unused trial medication and empty packaging to each visit (number of tablets taken & number of tablets missed will be recorded), this will be collected, and a new supply will be given. All medications will be recorded. Compliance will be verified. The patient will be asked to bring unused trial medication and empty packaging to each visit, this will be collected, and a new supply given every 3 month.
Adverse events & Adverse pregnancy events	Enquiry about adverse events including adverse pregnancy events. In case the patient has miscarried an 'adverse pregnancy events' form has to be filled out (not SAE).

PREGNANCY follow up visit 3 3 rd Trimester visit (Gestational week 27 – end of pregnancy)	
US growth scans	Depending on the individual patient one or more US scans have been performed so far. All available growth scan results will be recorded. Information will be obtained from maternity records. If uterine artery Doppler results have not been documented at previous visit, they should be recorded.

Adverse events & Adverse pregnancy events	Enquiry about adverse events including adverse pregnancy events. In case the patient has miscarried an 'adverse pregnancy events' form has to be filled out (not SAE).
Medication	 All medications will be recorded. Compliance check (Kit number to be noted, date of current kit started & ended, number of tablets taken, number of tablets missed) IMP dispensation
	The patient will be asked to bring unused trial medication and empty packaging to each visit (number of tablets taken & number of tablets missed will be recorded), this will be collected and a new supply will be given.
Post delivery	In case of preterm delivery, record actual date and mode of delivery, gestational age, gender, birth weight, Apgar score, neonatal morbidity (neonatal haemorrhage or thrombotic complications, infections, congenital abnormalities) neonatal days in special care, days to discharge from hospital following delivery (mother and child).

POST PARTUM follow up visit		
Post partum visit (up to 6 weeks post partum)		
Mother	None	
Child	 Record actual date and mode of delivery Gestational age Child gender Birth weight Apgar score Neonatal morbidity (bleeding or thrombotic complications, infections, congenital abnormalities, days in special care) Days of admission (mother & child). 	
US growth scans	Selected centres: bloods for additional research Depending on the individual patient one or more US scans have been performed during pregnancy. All available growth scan results will be recorded. Information will be obtained from maternity records.	
Medication	 All medications will be recorded. Compliance check (Kit number to be noted, date of current kit started & ended, number of tablets taken, number of tablets missed) The patient will be asked to bring unused trial medication and empty packaging (number of tablets taken & number of tablets missed will be recorded). 	
Adverse events & Adverse pregnancy events	 Enquiry about adverse events including adverse pregnancy events. In case the patient has had a miscarriage this will be noted in the patient notes and the eCRF (not SAE). 	

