4.1.2 Secondary endpoints

The pre-defined secondary endpoints include:

The pre-defined secondary endpoints include:

- 1. Pregnancy loss < 10 weeks gestation
- 2. Pregnancy loss > 10th week of gestation of a morphologically normal fetus documented by ultrasound or by direct examination of the fetus
- 3. Premature birth of a morphologically normal neonate < 34 weeks due to any of: pre-eclampsia, eclampsia, recognized features of placental insufficiency.
- 4. Gestational age at delivery
- 5. Birth weight
- 6. Delivery by Caesarean section
- 7. Apgar score < 7 at 5 min
- 8. Neonatal morbidity (bleeding or thrombotic complications, infections, congenital abnormalities)
- 9. Days to hospital discharge following delivery (mother & child)
- 10. Thrombotic events in the mother during pregnancy and 6 weeks post-partum.
- 11. Days of neonate in special care
- 12. Safety and tolerability of hydroxychloroquine in the mother and in the neonate

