4.3 Trial Flowchart

HYPATIA trial study procedures

	Pre-pregnancy		Pregnancy			Post- partum	
	Screening visit*	Baseline visit*	Pre- pregnancy visits §	1st Trimester	2nd Trimester	3rd Trimester	Post- partum visit†
Written informed consent	x	-					
Demographics	x						
Eligibilty assessment (1)	x	x					
Past medical history (2)	x						
Smoking history	x				x		
Past pregnancy history (3)	x						
Current medication	x	x	x	x	x	x	x
Height	x	~	~	~	~	~	~
Weight	x						
- · · · · · · · · · · · · · · · · · · ·							
Collection of blood results (4)	X						
Blood pressure & Pulse	X						
Urine dip	X						
Randomisation		X					
Dispensation IMP		X	X	X	X	X	
Adverse events monitoring		X	X	X	X	X	X
Physical exam (incl stetoscopy)	X		X	x	X	X	
Blood sample (5)	X		X	X	X	X	
Info about current pregnancy (6)			~	X	X	X	
Compliance check (7) Blood for additional research (8)		×	X	x x	X	x	x
Growth scans		X	X	*	x x	x	X
Uterine Artery Doppler (20-24 weeks)					x (9)	^	^
Child gender					× (9)		x
Birth date							x
Child APGAR at 5 min							x
Days of admission (mother&child)							x
Gestational age							x
Mode of delivery (Cesarean Y/N)							x
Birth weight							x
Neonatal morbidity (neonatal bleeding or thrombotic complications, infections, congenital abnormalities, days in neonatal special care)							x
* These visits can all be completed on the same	day. Consen	t within 3 mo	onths.				
§ Visits every 3 months until patient pregnant, th max 4 times (a total of 12 months)	en new dispe	nsation of s	tudy drug and	dispensation	every 3 mor	nths. Pre-preg	nancy visits
† Follow up visit should be completed within 6 we can contact the participant to obtain the study inf		atient is una	ble to attend c	linic within th	e timeframe	of 6 weeks, tl	ne study team
(1) Eligibility assessment: persistent presence of	aPL twice 12	2 weeks apa	rt, ENA negati	ve			
(2) Past medical history as per exclusion criteria other significant past medical history. Blood sam antibodies. Blood results can be obtained from re screening as per standard of care.	nple review (F	BC, kindne	y and liver pro	file) and resu	Its will be co	llected: aPL a	ntibodies, ENA
 (3) Past pregnancy history - to record in chronolo premature birth < 34 due to pre-eclampsia, eclar 						s, miscarriag	e > 10 weeks,
(4) max 12 months old (antiphospholipid antibod	ies (aPL) type	e and titres i	incl local cut of	f, ENA antibo	odies). Repe	at aPL if need	led.

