Follow up visits for the HYPATIA study purpose will be scheduled once every trimester (defined as 1st, 2nd and 3rd trimester visits), however, if the participant required closer monitoring she will be followed up accordingly as per standard of care. Women will be instructed to stop trial medication on the day of delivery and will be asked to hand in the rest of the trial medication at their post-partum follow up. The post-partum visit shall be completed 6 weeks post-partum. For some women it may be difficult to attend a follow up visit within 6 weeks after delivery (due to sleep deprivation or other challenges with a newborn) and the study teams can therefore contact the patient post-delivery to collect outcome data (date of delivery & information about the child). This can be decided on an individual basis.

All eligible women will have been diagnosed with persisting antiphospholipid antibodies (aPL) prior to trial entry. Results of aPL, i.e. anticardiolipin IgG and IgM antibodies, beta2glycoptroteinI IgG and IgM antibodies and lupus anticoagulant, confirming their presence or a diagnosis of APS. For the purpose of the HYPATIA study the last positive test must be within 12 months of study entry. The dates when the tests were performed routinely at the trial sites have to be documented in the notes and recorded in the eCRF.

Patients with anticardiolipin (IgG or IgM) antibodies and/or beta2glycoptroteinI (IgG or IgM) antibodies above the 95th percentile are considered positive and the levels will be recorded in the CRF. Each site will be asked about their local normal ranges (i.e. the local cut off for the 95th percentile) for anticardiolipin (IgG or IgM) antibodies and/or beta2glycoptroteinI (IgG or IgM) antibodies, which also have to be recorded in the patient notes and eCRF.

For the purpose of the HYPATIA study blood test results from prior to entering the trial can be used and for the purpose of the HYPATIA study with two specifications:

- the last positive aPL test result must be within 12 months of study entry
- Other blood results such as full blood count, kidney and liver function must be within 3 months of study entry.

We accept past positive antiphospholipid antibody screens as valid, as long as they have a positive screen within 12 months of study entry and if there is physical evidence of such in the patients' records.

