8.1.1 Primary Efficacy Parameters

The primary efficacy parameters will include the absence of pregnancy complications, i.e. as defined in the primary endpoint is defined as follows:

The primary endpoint is a composite of three principal aPL-related adverse pregnancy outcomes: one or more pregnancy loss(es) (either < 10 weeks gestation or beyond 10 weeks of gestation of a morphologically normal fetus documented by ultrasound or by direct examination of the fetus) and premature birth of a morphologically normal neonate before 34 weeks due to any of: pre-eclampsia, eclampsia, recognized features of placental insufficiency Premature birth for other reasons will not be included.

The components of the primary endpoint will each be presented as secondary endpoints (below).

The pre-defined secondary endpoints include:

- 1. Pregnancy loss < 10 weeks gestation
- Pregnancy loss > 10th weeks of gestation of a morphologically normal fetus documented by ultrasound or by direct examination of the fetus
- 3. Premature birth of a morphologically normal neonate < 34 weeks due to any of: pre-eclampsia, eclampsia, recognized features of placental insufficiency.
- 4. Gestational age at delivery
- 5. Birth weight
- 6. Delivery by Caesarean section
- 7. Apgar score < 7 at 5 min
- 8. Neonatal morbidity (bleeding or thrombotic complications, infections, congenital abnormalities)
- 9. Days to hospital discharge following delivery (mother & child)
- 10. Thrombotic events in the mother during pregnancy and 6 weeks post-partum.
- 11. Days of neonate in special care
- 12. Safety and tolerability of hydroxychloroquine in the mother and in the neonate

The components of the primary endpoint will each be presented as secondary endpoints.

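### The only post-partum contact may take place before the 6-week maternal thrombosis window has closed

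*Protocol*

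**What the plan says.** The endpoint in section 4.1.2, repeated in the synopsis and section 8.1.1, is "Thrombotic events in the mother during pregnancy and 6 weeks post-partum". The sections that decide when the last observation is made differ:

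- Section 7.1, visit table: "Post partum visit (up to 6 weeks post partum". The row for the mother reads None. A separate row provides "Enquiry about adverse events including adverse pregnancy events", and medications and days of admission for mother and child are also recorded.
- Section 4.3, flowchart footnote: the visit should be completed within 6 weeks. For a woman who cannot attend in that time, the study team "can contact the participant to obtain the study inf" (the word is cut off in the extracted text).
- Section 6.3: "The post-partum visit shall be completed 6 weeks post-partum". Where attendance is difficult, "the study teams can therefore contact the patient post-delivery to collect outcome data (date of delivery & information about the child".
- Section 6.6: participation runs to delivery, with a maximum of 21 months.

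The same contact records two hospital-stay endpoints: "Days to hospital discharge following delivery (mother & child" and "Days of neonate in special care". Neither has a stated closing date.

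**The concern.** An endpoint with a fixed window needs an observation at or after the end of that window. Here the last scheduled contact has a latest date but, in two of the three places that time it, no earliest date. One description of the fallback does not mention the mother at all. A site that sees a woman at week 2 has complied with section 7.1 and has no further scheduled occasion to learn of a thrombosis in weeks 3 to 6. An analyst would then have no means of telling a woman without an event from one not asked after the event could have happened. At stake is the completeness of a secondary endpoint that matters to this trial, since the background section gives antithrombotic action as part of the rationale for hydroxychloroquine.

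**Working it through.** The protocol states no figure for this point, so there is none to reproduce. The check sets the sections against the endpoint and measures the gap.

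**Step 1. Timing against the endpoint window (closes 6 × 7 = 42 days after delivery)**

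| Section | Timing of last contact | Guarantees observation to day 42? |
|---|---|---|
| 7.1 visit table | any time to 6 weeks | no |
| 4.3 footnote | within 6 weeks | no |
| 6.3 visit | at 6 weeks | yes |
| 6.3 fallback | after delivery, no date | no |
| 6.6 participation | ends at delivery | no |

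The 21 months in section 6.6 are the 12-month conception limit plus about 9 months of pregnancy, so the six post-partum weeks lie outside the stated participation period.

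**Step 2. Size of the gap at that contact**

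For a last contact at week *w*, the share of the post-partum window with no scheduled enquiry is (6 − *w*)/6:

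- week 1: 5/6 = 83%
- week 2: 4/6 = 67%
- week 3: 3/6 = 50%
- week 4: 2/6 = 33%
- week 5: 1/6 = 17%
- week 6: 0%

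These are shares of time, not of events. The protocol gives neither a post-partum thrombosis rate nor an expected distribution of contact dates, so the number of missed events cannot be calculated.

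**Step 3. Other routes by which an event could be found**

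- Section 7.1, adverse event enquiry: made at the contact itself, so it covers only the time up to it.
- Section 6.5: adverse events are followed to the end of the trial, but no contact is scheduled at which a new one would come to light.
- Section 8.2: lists puerperal thrombosis among the outcome information and describes how suspected events are evaluated and how details are retrieved from the treating centre. It sets no date for asking.
- Section 9.2: events that are outcome measures go on the appropriate CRF and not through serious adverse event reporting, so that route is not a dependable backstop.

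**Step 4. Hospital days**

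Discharge age is not in the documents. Assume discharge at a postmenstrual age of 35, 37 or 40 weeks. Stay = (discharge age − gestational age at birth) × 7. For a birth at 26 weeks:

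- (35 − 26) × 7 = 63 days, of which 63 − 42 = 21 fall after day 42
- (37 − 26) × 7 = 77 days, of which 35 fall after day 42
- (40 − 26) × 7 = 98 days, of which 56 fall after day 42

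On the same assumptions, an infant is still in hospital at a 6-week contact if born before 29, 31 or 34 weeks. Such a count is incomplete at the contact and has to be finished from another source.

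**The case against.** The strongest reply is that the protocol already covers the mother. The attended visit asks about adverse events, records all medication (which would reveal new anticoagulation) and records her days of admission. The flowchart fallback covers study information generally and is triggered by inability to attend within 6 weeks, so it would tend to fall late. Section 8.2 names puerperal thrombosis explicitly, and section 6.3 does place the visit at 6 weeks. The eCRF is not shown and may contain a thrombosis item. All of this stands, and it means that late events can be missed, not that they will be. It does not supply a scheduled enquiry covering the whole window.

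Three stronger readings are tempting, and the documents do not support them.

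- A reader might infer that ascertainment differs by arm because women with a loss receive no 6-week contact. Audit live births of 67% and 57% would give complements of 33% and 43%, a 10-point difference. But section 7.1 foresees noting a miscarriage at the post-partum visit and refers women who miscarry to a next follow-up visit. What is missing is the date of that visit and whether a post-partum window applies to a loss. The complement of a retrospective live-birth rate is also too crude to carry a bias claim.
- A reader might infer that neonatal stay is cut off at day 42. Those endpoints have no closing window, nothing caps the record, and section 8.2 provides access to the child's hospital notes if needed.
- A reader might infer that the contact concerns only the child. That describes the section 6.3 fallback, not the attended visit.

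**Conclusion.** The point holds in a limited form. Sections 4.3, 6.3, 6.6 and 7.1 do not agree on when follow-up of the mother ends, and followed as written they permit a last contact before the window of endpoint 10 closes. The uncovered share is 0% at week 6, 67% at week 2 and 83% at week 1. The contact weeks are illustrations, since actual contact dates are not known. The conclusion rests on there being no scheduled enquiry after the post-partum contact, and the protocol shows none. An unseen eCRF thrombosis item would improve the question but not its timing.

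For hospital days the point is smaller: completion from the notes is allowed but not required. The primary composite is unaffected. This should be corrected, but it does not threaten the trial's main conclusion.

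**What to change.** 1. Amend sections 4.3, 6.3, 6.6 and 7.1 so that the existing post-partum contact, in clinic or by telephone, takes place at or shortly after day 42, and participation extends to it. The uncovered share then becomes 0%.
2. Have that contact, including the telephone fallback, ask explicitly about maternal thrombosis: yes or no, and the date.
3. State whether the 6-week window applies after a pregnancy loss and, if so, from what date it runs.
4. For infants still in hospital at the contact, require special-care and discharge days to be completed from the hospital notes to which section 8.2 already gives access.

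The cost is an amendment to the wording, one eCRF item if none exists, a slightly later contact and a short call for some women, and a later look at the notes for the few infants still admitted. No extra clinic visit is needed.
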